The adapted SPIRIT intervention (SPIRIT-dementia) sessions lasted 100 minutes on average (range, 51-122). The main reasons for the longer duration compared to earlier SPIRIT studies (on average 82 minutes) were that the interventionist was required to: a) speak slowly, b) repeat questions for the PWD, and 3) ask clarifying questions whenever the PWD's response was vague. As is typical with PWD there is slowing of speech and the PWDs often paused to come up with words or collect their thoughts, and the interventionist was prohibited from rushing, interrupting, or finishing the sentence for the PWD. Although the intervention could have been broken down to two sessions, as in previous SPIRIT with other patient populations, we determined that a single session approach would be more appropriate due to PWD's limited or absent short-term memory.

Supplement Cohort Study:

End-of-life preferences of patients with serious illnesses are generally stable. A recent systematic review¹⁰ of evidence on the stability of end-of-life preferences over time found that more than 70% of patients' preferences for end-of-life care were stable over time, and preference stability was generally greater among inpatients and seriously ill outpatients than among older adults without serious illnesses ($p<.002$; $N=55$ studies; 24 studies for metanalysis). Further, patients who completed advance directives had more stable preferences than those who did not, suggesting that efforts to engage patients in actively thinking about these decisions can augment stability of preferences for treatment over time. These findings support that previously stated preferences for end-of-life care may be sufficiently stable to guide current care.

Disasters, psychosocial impact, and decision making behaviors: According to the National Oceanic and Atmospheric Administration,¹⁹ over the past 4 decades, the U.S. has been affected by 219 natural disasters where the overall damage costs exceeded in inflation-adjust \$1 billion, and 10,000 lives were lost. Recently, the COVID-19 pandemic, one of the most devastating disasters, has killed 100,000 Americans in less than 4 months (as of May 2020)²⁰ and caused 4 million job losses nationwide.²¹

Because disasters are typically unexpected, sudden, and overwhelming, it is common for people who have experienced one to have strong psychological responses, and their behaviors are affected in the short and possibly longer term.^{22,23} Studies^{24,25} have shown that following disaster, people frequently feel disoriented or unable to integrate distressing information, and once these initial reactions subside, people can experience a variety of thoughts and behaviors, such as intense or unpredictable feelings of nervousness or grief, disruptive sleep and eating patterns, strained interpersonal relationships with increased conflict and disagreements with family members, and disengagement from seeking social support. Shortly after the 9/11 terrorist attack, a national survey²⁶ found that heightened levels of posttraumatic stress were not limited to New York city and surrounding areas but across the country, suggesting that the psychological impact of a disaster may not require direct exposure to the disaster.

There is great interest in elucidating the effects of disaster for different racial groups especially in light of the disproportionate health disparities in COVID-related hospitalization rates and deaths in Blacks across the US. We briefly discuss 2 studies that did not concern disasters but that sheds light on why race is an important consideration in our proposed aims. Rosen et al.²⁷ found that Blacks, compared to Whites, were more risk tolerant even after adjusting for educational status. Specifically, Blacks were more willing to live with the risks of their underlying disease and undergo fewer procedures and that Blacks would accept much larger risks to avoid an invasive procedure compared to Whites. They also found that White race, lower education, and female sex were associated with a higher likelihood of risk aversion. On the other hand, from a different study, Blacks and Hispanics are far less likely to invest in the stock market (more risk averse in terms of investing behaviors) than

Whites, and low-income Whites are far more likely to invest in the stock market than Blacks or Hispanics regardless of income.²⁸

Although the literature on economical and psychosocial impact of disasters is growing, we have very little empirical data to guide ACP with our sickest patients during a disaster. Via this new research, we seek to learn whether a disaster would make patients with a serious chronic illness more or less likely to want aggressive treatment. We posit that the effects of a disaster bring doubt to clinicians as well as families regarding how to interpret an advance directive or end-of-life care preferences expressed some time ago before the pandemic. We will generate empirical data on the impact of the COVID-19 pandemic on patients' end-of-life preferences, to address whether the stability of preferences is disrupted by the pandemic, and to identify patient characteristics, including race/ethnicity, associated with pre-/post-pandemic changes.

2.3 RISK/BENEFIT ASSESSMENT

2.3.1 KNOWN POTENTIAL RISKS

As the SPIRIT intervention has proven to be safe and efficacious, this Phase III pragmatic trial involves very minimal or low risk. Patient and surrogate participants may experience an emotional reaction (e.g., anxiety) or fatigue during the intervention or data collection. In our previous studies,¹⁷⁻²⁰ intervention dyads were less apprehensive and more satisfied with the quality of communication than control dyads. It is expected that psychological burden caused by the SPIRIT intervention will be less than or equal to that of usual care.

2.3.2 KNOWN POTENTIAL BENEFITS

Findings from our previous studies indicate benefits of the SPIRIT interventions for participants in the intervention group, including meeting needs to plan for future medical care and sharing values and beliefs. In addition, in our recent study, surrogates in the intervention group perceived the intervention to be highly beneficial during end-of-life decision making for their loved ones and surrogates showed significantly lower post-bereavement distress symptom scores.

2.3.3 ASSESSMENT OF POTENTIAL RISKS AND BENEFITS

As described above, it is expected that psychological burden caused by the SPIRIT intervention will be less than or equal to that of usual care. Previous studies have demonstrated the potential benefits of SPIRIT.

3 OBJECTIVES AND ENDPOINTS

The objective of this multicenter, clinic-level cluster randomized trial is to evaluate the effectiveness of SPIRIT delivered by dialysis care providers as part of routine care in free-standing outpatient dialysis clinics compared to usual care plus delayed SPIRIT implementation. Simultaneously, we will evaluate the implementation of SPIRIT, including sustainability. We will use a Type I effectiveness-implementation hybrid approach^{62,63} that combines testing intervention effectiveness and gathering information about implementation of an efficacious intervention in a real world setting. The short-term goal is to generate sufficient evidence to accelerate the integration of SPIRIT into dialysis practice and policy. We will recruit 400 dyads of patients at high risk of death in the next year and their surrogates from 30 dialysis clinics in 4 states.

OBJECTIVES	ENDPOINTS	JUSTIFICATION FOR ENDPOINTS
Primary		

OBJECTIVES	ENDPOINTS	JUSTIFICATION FOR ENDPOINTS
Examine the effectiveness of SPIRIT compared to usual care on preparedness outcomes for end-of-life decision making (defined as dyad congruence on goals of care, patient decisional conflict, and surrogate decision-making confidence) at 2 weeks post-intervention.	Dyad congruence on goals of care (binary); Patient decisional conflict (scale); Surrogate decision-making confidence (scale) Composite outcome (goals-of-care congruence with confident surrogate; binary)	The primary goal of SPIRIT is to prepare the patient and surrogate for end-of-life decision making. The preparedness outcomes will indicate whether or to what extent SPIRIT accomplished the goal.
Secondary		
Examine the effectiveness of SPIRIT and usual care on surrogates' post-bereavement distress	Anxiety symptom score (HAS-anxiety); Depression symptom score (HAS-depression); Post-traumatic distress symptom score (PTSS)	Surrogate prepared by SPIRIT for EOL decision making should experience less post-bereavement distress.
Evaluate the process outcomes of SPIRIT implementation: during the initial and delayed implementation of SPIRIT	Acceptability, fidelity, intervention costs, and sustainability	Descriptive aim to generate data for translation
Tertiary/Exploratory		
Examine the effectiveness of SPIRIT and usual care on EOL treatment intensity	Health care utilization (percentages of patients hospitalized, having ICU admission, and having intensive procedures, and LOS)	To examine whether SPIRIT reduces aggressive EOL treatment
Supplement		
Estimate the effects of the SPIRIT-dementia intervention on the preparedness outcomes and care decisions	Dyad congruence on goals of care (binary); Patient decisional conflict (scale); Surrogate decision-making confidence (scale) Composite outcome (goals-of-care congruence with confident surrogate; binary) Care decisions (withdrawal from dialysis, Do-Not-Resuscitate order, hospice enrollment)	The primary goal of SPIRIT is to prepare the patient and surrogate for end-of-life decision making. The preparedness outcomes will indicate whether or to what extent SPIRIT accomplished the goal. Care decisions will reflect the effects of SPIRIT on end-of-life decision making.
Estimate the effects of the SPIRIT-dementia intervention on surrogates' post-bereavement distress	Anxiety symptom score (HAS-anxiety); Depression symptom score (HAS-depression)	Surrogate prepared by SPIRIT for EOL decision making should experience less post-bereavement distress.
Supplement cohort study (non-clinical trial)		
Assess the effect of the pandemic on the stability of end-of-life care preferences and on our key outcomes (dyad congruence on goals of care, patient decisional conflict, and surrogate decision-making confidence).		

Measurement and data collection time points

Outcome	Measure	Completed by			Time points
		pt	srgt	prov	
Effectiveness outcome evaluation					
Preparedness					
Dyad congruence	Goals-of-Care Tool (2 end-of-life scenarios)	✓	✓		Baseline and 2 wks
Patient decisional conflict	Decisional Conflict Scale (range, 1-5)	✓			Baseline and 2 wks
Surrogate decision-making confidence	Decision Making Confidence Scale (range, 0-4)		✓		Baseline and 2 wks
Overall preparedness	Preparedness for End-of-Life Decision Making (range, 26-104)	✓	✓		Baseline and 2 wks
Post-bereavement distress	HADS (each subscale range, 0-21) PTSS-10 (range, 10-70)		✓		Baseline and 3 mo. after patient death
End-of-life care intensity	Percentages of patients hospitalized, having ICU admission, and having intensive procedures and length of hospital stay				Medicare claims data after patient death
Initial implementation process evaluation					
Care provider acceptability	Dialysis care provider's perceived acceptability (range, 7-28); Semi-structured interview			✓	End of the initial implementation
Patient & surrogate acceptability	Patient and surrogate acceptability (range, 10-40 each)	✓	✓		2 wks
Fidelity	SPIRIT provider's coverage of the SPIRIT components and durations; Brief patient and surrogate survey	✓	✓	✓	SPIRIT provider after each SPIRIT completion Patient and surrogate at 2 wks
Intervention costs	The actual time the care provider spent in carrying out SPIRIT, multiplied by hourly wage (+benefits), plus costs of materials				End of the early implementation
Sustainability	Brief semi-structured interview		✓		End of 12 mo. post 9-month follow-up
Delayed implementation process evaluation					
Care provider acceptability	Dialysis care provider's perceived acceptability (range, 7-28); Semi-structured interview			✓	End of the delayed implementation
Fidelity	SPIRIT provider's coverage of the SPIRIT components durations			✓	SPIRIT provider after each SPIRIT completion
Intervention costs	The actual time the care provider spent in carrying out SPIRIT, multiplied by hourly wage (+benefits), plus costs of materials				End of the delayed implementation
Descriptors and potential covariates					
Sociodemographics	Sociodemographic Profile	✓	✓		Baseline for patients and surrogates
				✓	End of the initial implementation for clinicians
Clinical characteristics	Medical Profile				Baseline
Clinic-level contextual data	Contextual Data Collection Form				End of each implementation
Usual care	Documented AD completion on the Plan of Care form; presence of DNR, POLST, or MOST (from EMR)				Baseline and 6 mo.

Pt, patient; Srgt, surrogate; Pro, care provider

[figure not shown]
Data collection highlighted in yellow is performed locally.

For supplement aims:**Measurement and data collection time points**

Outcome	Measure	Completed by		Time points
		pt	srgt	
Estimating the effects of SPIRIT-dementia				
Preparedness				
Dyad congruence	Goals-of-Care Tool (2 end-of-life scenarios)	✓	✓	Baseline and 2-3 days
Patient decisional conflict	Decisional Conflict Scale (range, 1-5)	✓		Baseline and 2-3 days
Surrogate decision-making confidence	Decision Making Confidence Scale (range, 0-4)		✓	Baseline and 2-3 days
Overall preparedness	Preparedness for End-of-Life Decision Making (range, 26-104)	✓	✓	Baseline and 2-3 days
Post-bereavement distress	HADS (each subscale range, 0-21)		✓	Baseline and 1 mo. after patient death
Care decisions	Percentages of patients hospitalized, having ICU admission, and having intensive procedures and length of hospital stay	CMS form 2746		After patient death

[figure not shown]
4 STUDY DESIGN**4.1 OVERALL DESIGN**

We will conduct a dialysis clinic-level cluster randomized trial with two groups, SPIRIT versus usual care followed by delayed SPIRIT. We will recruit 400 dyads of patients on chronic (“prevalent”) dialysis who are at high risk of death in the next year and their surrogate decision-makers (total 800 individuals) from 30 free-standing dialysis clinics in 4 states. The primary outcomes are patient and surrogate self-report preparedness for end-of-life decision making. The implementation evaluation data will be obtained throughout the study course. Upon patient death (anticipate 20% of patients; n = ~ 80), we will assess surrogates’ post-bereavement distress. Patient participation will end at 9 months (to allow for obtaining Medicare claims data during the study period) or death, whichever occurs first; surrogate participation will end at 9 months or at the completion of 3-month post-death follow-up. If patient is still living at 9 months, we will ask for an extension of follow up period to include 12 more months. Medicare claims data for end-of-life treatment intensity will be obtained quarterly. Clinics assigned to usual care will receive the delayed implementation, SPIRIT, in Year 4, Q1. This is a Phase III trial of an intervention that involves minimal risks and has proven to be efficacious, and thus no interim analysis is planned.

For Supplement Aims:

We will use a randomized controlled trial design with two groups: SPIRIT-dementia and usual care. From the pool of screened but excluded ESRD patients, we will recruit 30 dyads of patients with mild to moderate dementia and their surrogates. The groups will be stratified by race (white vs non-white). Patient and surrogate self-reported preparedness for end-of-life decision making will be measured at baseline and shortly after the intervention (by phone in the next 2-3 days) as done in the pilot test of SPIRIT-dementia. Additionally, we will review the patient's medical record to examine care decisions at 6 months or after the patient's death, whichever occurs first. In the case of patient death, we will also assess surrogates' post-bereavement outcomes (anxiety and depression symptoms) at 1 month after the patient's death. Based on previous research,¹³ we anticipate about 50% of the supplement sample will die within 12 months of enrollment. All data collection from study participants will be telephone-based.

Supplement cohort study:

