Recruitment will occur over 24 months beginning at the end of Year 1. We are highly experienced in recruiting seriously ill ESRD patients and their surrogates for research. Consent rates in our previous studies have been consistent at approximately 84% despite the studies' focus on end-of-life, the requirement that both patient and surrogate participate, and long-term follow-up. We expect a similar if not higher consent rate because the study involves a shorter follow-up time and minimal data collection directly from patients and surrogates. Based on our previous studies,¹⁸⁻²⁰ we conservatively anticipate that 427 patients (20%) will be *eligible and willing* to participate. To reach 400 dyads, we expect to enroll 21-22 dyads per cluster on average. These clinics each accept 10-70 new patients each year (total 700 additional patients), and thus our recruitment goal is readily achievable.

To Maximize Participant Retention, strategies found effective in retaining dyads over 12 months (dropouts, 3.8%) in our efficacy trial²⁰ will be used: we will

- a) obtain two backup contacts from each member of the dyad in the event that we cannot reach them by telephone and mail
- b) make confirmation phone calls 2 days prior to each follow-up
- c) make monthly check-in calls
- d) send holiday cards
- e) assign the same data collector whenever possible
- f) compensate each member of the dyad with gift cards (\$15 at baseline, \$15 at 2 weeks for the preparedness outcome assessment; \$20 at 3 months for the post-bereavement outcome assessment). Consistent with a pragmatic trial, participants will not be compensated for participating in the intervention. The Emory Study Coordination Center will be responsible for disbursement.

For Supplement Aims:

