6.2 PREPARATION/HANDLING/STORAGE/ACCOUNTABILITY

6.2.1 INTERVENTIONIST TRAINING AND ACCOUNTABILITY

Care Provider Training for SPIRIT

The ideal individual to conduct ACP discussions is still unknown, but we believe it is not the profession per se but rather the willingness and appropriate training that make an individual suitable for conducting the discussions. Each dialysis clinic has identified a care provider designated to conduct SPIRIT sessions (e.g., ANP, RN, MSW). SPIRIT training will occur shortly after randomization for the initial implementation clinics and in early Year 4 for

the delayed implementation clinics. The SPIRIT trainers, trained and certified by the PI at the Study Coordination Center (at Emory), will conduct SPIRIT training for all four sites based on the manualized curriculum.

Care provider training will consist of a 1½-day, competency based program that has been used in our previous trials:

- Module 1 (1/2 day) to ensure understanding of end-of-life care issues and communication as key to improving end-of-life care and the Representational Approach (theoretical underpinnings of SPIRIT);
- Module 2 (1/2 day), as skill-base session to gain understanding of the SPIRIT intervention and delivery, including role plays. A 2-week practice period will be scheduled for integration of skills and exploration of additional learning needs; and
- Module 3 (1/2 day) for skill-demonstration and certification. These training sessions will be conducted in collaboration with the Emory Nursing Professional Development Center.

For Supplement Aims:

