Surrogates' post-bereavement psychological distress (at baseline and 3 mo. post patient death):

Symptoms of anxiety, depression, and post-traumatic distress^{42,73} will be measured using the Hospital Anxiety and Depression Scale (HADS)⁷⁴; subscale scores range from 0 to 21 with higher scores indicating greater symptom severity. Internal consistencies and test-retest reliabilities are 0.88–0.90 and 0.84–0.94, respectively.⁷⁵ Intensity of post-traumatic distress symptoms will be assessed using the Post-Traumatic Symptoms Scale-10 (PTSS-10).⁷⁶ Higher scores indicate more intense symptoms (range 10–70).⁷⁷ The PTSS-10 has been shown to have high sensitivity and specificity.^{76,78,79}

Implementation Process Outcomes

For the **initial SPIRIT intervention**, after the final dyads have completed the SPIRIT sessions (~Year 3, Q1), care providers will complete a survey and an interview.

- **Care provider acceptability** will be evaluated using the 7-item Care Providers' Perceived Acceptability Survey to assess their perceptions about SPIRIT implementation, including the time required, impact on interactions with patients, and whether they would recommend SPIRIT to other clinics.⁸⁰ Response options range from 1=strongly disagree to 4=strongly agree; higher scores indicate greater acceptability.
- **A brief (~15 min.) semi-structured interviews (face-to-face or by telephone; audio-recorded) will obtain providers' perspectives** on whether the implementation of SPIRIT is compatible with their setting and the workflow, its perceived utility, their willingness to continue using it after the study, factors influencing implementation (barriers, logistical constraints, and facilitators), and suggestions for improvement.
- **Patient and surrogate acceptability** will be assessed using the 10-item ACP Acceptability Questionnaire developed from our previous trial.²⁴ Participants are asked how strongly they agree or disagree (4 to 1) with statements about their experience with SPIRIT sessions, including duration, interactions with the care provider, level of comfort and satisfaction. Higher scores indicate greater acceptability. Each patient and surrogate will complete this survey at the 2-week post-intervention follow-up.

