- **Fidelity/adherence** will be assessed using two independent data sources, (a) the SPIRIT Interview Guide, Checklist, and self-evaluation completed by the care provider after each SPIRIT session and (b) patient and surrogate responses to the SPIRIT components coverage during the 2-week post-intervention follow-up as described above. The number of SPIRIT components covered, the minutes required for the care provider

to complete the sessions, the number of dyads who complete SPIRIT sessions, and the number of incomplete or interrupted sessions will be aggregated.

- **Intervention costs** will be estimated based on the actual time the care provider spent in carrying out SPIRIT, multiplied by hourly wage (+benefits), plus costs of materials. Overhead (e.g., facility) costs and research staff's time will not be included.
- We define **sustainability** as the extent to which a newly implemented intervention is maintained within a service setting's ongoing, stable operations.⁸¹ In Y4, Q4, we will conduct a brief interview with SPIRIT care providers to ask about sustainability: (a) Is SPIRIT on-going (and at what frequency)? (b) What components of the SPIRIT protocol have been retained? and (c) Has SPIRIT implementation been evaluated at the clinic level? If so, how?⁸²

For the delayed SPIRIT implementation, the process evaluation will involve care providers only since patient and surrogate study participation will have ended at the end of 9-month follow-up or patient death. Care provider acceptability, fidelity, and intervention costs will be determined as described above.

End-of-life treatment intensity (upon patient death)

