9.4.3 ANALYSIS OF THE SECONDARY ENDPOINT(S)

Analysis of secondary endpoints are not dependent on findings of primary endpoints.

SPIRIT effectiveness on surrogates’ post-bereavement psychological distress: We will use the same approach as in the analysis of the primary endpoints to compare anxiety, depression, and post-traumatic distress symptoms in SPIRIT vs usual care among surrogates of patients who die during the initial implementation and 9-month (or extended) follow-up.

Implementation process outcomes: Quantitative data on acceptability, fidelity, and costs of SPIRIT will be summarized using descriptive statistics. SPIRIT will be determined to be acceptable to care providers and patients and surrogates if over 75% of responses exceed an average summative score ≥ 3 (of 4) on the acceptability measures. Cost estimates will be used to ascertain resources needed to implement or replicate SPIRIT in the

future.⁹² We will also explore the relationships of these quantitative data with characteristics of settings and stakeholders. Transcripts of acceptability interviews will be transferred to ATLAS.ti for analysis. Content analysis techniques⁹³ will be used without preconceived categories.⁹⁴ Open coding will be applied⁹⁵ and disagreements on coding will be resolved by consensus. We will examine the data for patterns or differences in themes between those with acceptability scores ≥ 3 and scores < 3 and setting characteristics. This analysis will be facilitated by creating matrixes that organize textual and numeric data for comparing and contrasting⁹⁶ so that what contributed to acceptability scores that are positive and less than positive may be identified. We will use a similar approach, content analysis, to evaluate the sustainability data.

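### The 12-month extension keeps control dyads under observation after SPIRIT reaches their clinics, and the plan does not say how those dyads or their later deaths are handled in Aims 3 and 4

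*Combined protocol and SAP*

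**What the plan says.** - **Rollout.** Section 4.1: "Clinics assigned to usual care will receive the delayed implementation, SPIRIT, in Year 4, Q1". Section 6.2.1 agrees on training: "SPIRIT training will occur shortly after randomization for the initial implementation clinics and in early Year 4" for the delayed clinics.
- **Follow-up.** Section 4.1 first sets an end: "Patient participation will end at 9 months (to allow for obtaining Medicare claims data during the study period) or death, whichever occurs first". It then adds: "If patient is still living at 9 months, we will ask for an extension of follow up period to include 12 more months". The synopsis (1.1) repeats the extension for patients and surrogates.
- **Deaths counted.** Section 9.4.3 compares surrogates of "patients who die during the initial implementation and 9-month (or extended) follow-up". Section 9.4.9 counts deaths during initial implementation and follow-up for Aim 4, with no cut at rollout. Section 9.3 makes every analysis intention-to-treat on all available data.
- **Separation.** Section 8.1 says the delayed-phase evaluation uses care providers only, "since patient and surrogate study participation will have ended at the end of 9-month follow-up or patient death". It does not mention the extension.
- **Recruitment.** Section 5.5: "Recruitment will occur over 24 months beginning at the end of Year 1". Section 8.1 instead dates the provider survey "after the final dyads have completed the SPIRIT sessions (~Year 3, Q1").

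**The concern.** The delayed design works as a comparison only while control clinics deliver usual care. Section 4.2 describes that order: usual care first, SPIRIT afterwards. The extension breaks the order for any control patient still being followed in Year 4.

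The protocol takes contamination through clinic staff seriously elsewhere. Section 4.2 gives it as a reason for cluster randomization, and section 6.3 merges clinics that share a SPIRIT provider. The rollout trains the staff of the control clinics themselves, and under section 5.5 the provider chosen to deliver SPIRIT usually also lists the eligible patients. An enrolled control dyad could therefore receive SPIRIT, and a later death would still be analysed as a usual-care death. If SPIRIT works, that narrows the difference between arms. The amendment history (10.2) gives the shortage of deaths for the secondary aims as the reason for the extension, so the deaths it adds are the ones most open to exposure.

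**Working it through.** **Step 1. The plan's own figure.** Section 9.2 gives power for anxiety (difference 1.35, variance 7.0, 19 clusters) of 0.84 at ICC 0.01 and 0.80 at ICC 0.03. With N deaths in equal arms:

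- cluster size m = N/19; design effect DE = 1 + (m - 1) x ICC
- SE = sqrt(7.0 x DE x 4/N); power from a noncentral t with 17 df, two-sided alpha 0.05

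For N = 160 (section 8.1): m = 8.42. At ICC 0.01, DE = 1.074, SE = 0.434, 1.35/SE = 3.11 and power is 0.83. At ICC 0.03, DE = 1.223, SE = 0.463, ratio 2.92 and power is 0.79. Both are close to the table. With the 80 deaths of section 4.1, power is 0.56 and 0.54, so the table fits about 160 deaths. No dropout is applied here, because the plan does not give its rate.

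**Step 2. Calendar.** Year 4, Q1 is months 36-39. Assumption: T2, from which the monthly calls run, falls 1.5 months after enrolment.

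| Last enrolment | Last T2 | 9 months ends | 21 months ends |
|---|---|---|---|
| Month 26 (from 8.1) | 27.5 | 36.5 | 48.5 |
| Month 27 (from 8.1) | 28.5 | 37.5 | 49.5 |
| Month 36 (from 5.5) | 37.5 | 46.5 | 58.5 |

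On the shorter timeline the base 9 months ends at about the start of rollout. On the longer one it runs well past it. The 21-month follow-up overlaps on both.

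**Step 3. Share of control deaths after rollout.** Assumptions: uniform enrolment from month 12; constant hazard h = -ln(1 - p)/9 with p = 4% (close to the figure in the amendment history) or 20% (the figure in 4.1) per 9 months; rollout R at month 36 or 39; a fraction u of dyads extends. For a dyad with T2 at s and follow-up length L:

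- P(death) = 1 - exp(-hL)
- P(death after R) = exp(-ha) - exp(-hL), where a = R - s, limited to the range 0 to L

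Both are averaged over s and weighted (1 - u) for L = 9 and u for L = 21. The share is the second over the first.

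| Enrolment ends | None extend | Half extend | All extend |
|---|---|---|---|
| Month 26 | 0.0-0.1% | 8.5-18.0% | 12.7-25.8% |
| Month 27 | 0.0-0.8% | 9.8-19.8% | 14.6-28.1% |
| Month 36 | 12.4-24.9% | 26.9-41.8% | 34.0-49.3% |

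The low end is R = 39 with 20% mortality; the high end is R = 36 with 4%.

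Hand check: at low mortality, deaths track person-time. For enrolment to month 36, all extending and R = 36, T2 is uniform on 13.5-37.5. Mean follow-up after month 36 is (21 x 21/2)/24 + 1.5 x 21/24 = 9.19 + 1.31 = 10.5 of 21 months, or 50%, against 49.3% in the table.

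**Step 4. What this could do to Aim 3.** In the extreme case, every control death after rollout was fully exposed and gained the whole effect. If these are a fraction f of control deaths, the difference becomes 1.35 x (1 - f). With 160 deaths and ICC 0.01, power falls from 0.83 to 0.75 (f = 10%), 0.65 (20%) or 0.54 (30%). This is a bound, not a forecast.

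**The case against.** Four points deserve weight.

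1. **The section 8.1 sentence explains why only providers are evaluated; it does not argue for overlap.** This is right. With section 4.2 it shows that follow-up was meant to finish first. The fault is a sentence not reconciled with the extension.

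2. **The shorter timeline fits the other dates better.** Final sessions in Year 3, Q1 plus 9 months gives Year 3, Q4, just before rollout. The section 3 measurement table puts the sustainability interview 12 months after that, which matches Year 4, Q4 in section 8.1. A reader might infer from section 5.5 that even the base 9-month follow-up runs well past rollout, but section 8.1 contradicts this and the documents do not settle it.

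3. **Time after rollout is not exposure.** A reader might infer that up to half of control deaths will be contaminated. The documents do not support that. The 49% needs the longer timeline, the earliest rollout and universal extension, yet extension needs fresh consent and no uptake is given. SPIRIT is a scheduled two-session intervention with a projected caseload of 1-2 dyads per cluster per month (6.1.1), and nothing says that enrolled control dyads would be chosen.

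4. **Some records will exist.** Delayed-phase fidelity data follow each completed SPIRIT (section 3 table), and preferences go into the medical record (6.1.1). No section links these to enrolled control dyads, so this answers the gap only in part.

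A reader might also infer that SPIRIT must be withheld from control dyads until observation ends. Section 4.2 justifies the delayed arm on ethical grounds, and that decision belongs to the investigators. The gap is that the protocol is silent.

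**Conclusion.** The point holds as an unreconciled overlap and a risk of dilution, not as demonstrated contamination. Extended follow-up of control dyads overlaps the rollout on either recruitment timeline. Overlap of the base 9 months is material only on the longer one.

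The size depends on two things the documents leave open: when enrolment ends and how many dyads extend. The step 3 ranges are upper limits on the share of control deaths that could be exposed, under uniform enrolment, constant hazard and the assumed T2 timing. Actual exposure could be far lower.

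Any bias would most likely be toward no difference, in Aim 3 (secondary) and Aim 4 (exploratory). The 2-week primary endpoints are essentially unaffected: only on the longer timeline with rollout at month 36 could control dyads enrolled in the last 1.5 of 24 months, about 6%, have T2 after rollout starts. The point is worth fixing because the remedy is cheap, but it does not threaten the main result.

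**What to change.** 1. Reconcile the participation sentence in 8.1 with 4.1 and 9.4.3, and the recruitment period in 5.5 with the final-session date in 8.1.
2. State in the protocol how enrolled control dyads still under observation are handled when their clinic starts SPIRIT. Section 8.1 notes that the delayed phase collects provider data only, so its evaluation does not depend on enrolled dyads.
3. Log each control clinic's start date and any SPIRIT session given to an enrolled control dyad.
4. Keep the intention-to-treat analysis of Aims 3 and 4. Add a pre-specified sensitivity analysis limited to deaths before rollout, with the same calendar cut-off in both arms (for example, the first control-clinic start date). SPIRIT clinics have no rollout date of their own, and truncating controls alone would give the arms unequal follow-up.

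The cost is protocol wording, a little record keeping and lower power in the sensitivity analysis. If 20% of 160 deaths are cut, N = 128 and the step 1 formula gives anxiety power of 0.75 instead of 0.83 at ICC 0.01, and 0.71 instead of 0.79 at ICC 0.03. For that reason it should support the intention-to-treat result, not replace it.
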